5.3 Study Endpoints and Statistical Plan

All endpoints will be determined according to an intention to treat analysis. The primary thrombotic endpoint will be platelet responsiveness (PRU) using the VerifyNow assay at 1 day post procedure. Platelet reactivity in the Clopidogrel and Ticagrelor groups will be compared

TABLE 1. Inclusion/Exclusion Criteria

Inclusion criteria:

- 1) Valvular heart disease and a clinical indication for TAVR,
- 2) Age of 18 years or older,
- 3) Capable of informed consent.
- 4) Planned transfemoral TAVR.

Exclusion criteria:

- 1) Prior history of stroke, transient ischemic attack (TIA), or intracranial hemorrhage,
- 2) Established bleeding diathesis or thrombocytopenia (<150k/dl),
- 3) End-stage renal disease,
- 4) Severe hepatic impairment or liver cirrhosis,
- 5) Pregnancy,
- 6) Current infection,
- 7) History of autoimmune disease,
- 8) Established allergy to contrast agents, thienopyridines, aspirin, or ticagrelor,
- 9) History of solid organ transplantation,
- 10) Atrial Fibrillation, DVT, PE or other indication for long term anti-coagulation,
- 11) Plan for direct aortic access or trans-apical TAVR,
- 12) Enrollment in another clinical trial,
- 13) Recent (< 12 months) or active excessive bleeding.

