using an independent samples t-test (or non-parametric test as appropriate), with significance declared for p-values <0.025 . The primary inflammatory endpoint is the percentage of inflammatory monocytes (compared to total monocytes) as a continuous variable 1 day after TAVR. The percentage of inflammatory monocytes in the Clopidogrel and Ticagrelor groups will be compared using an independent samples t-test (or non-parametric test as appropriate), with significance declared for p-values <0.025 . The percentage of inflammatory monocytes will also be compared over multiple time points to determine the trajectory and duration of the immune response, to guide duration of treatment in future studies. The values at baseline, 1 day, and 7 day will be compared within group using exploratory longitudinal mixed models to determine the kinetics of convalescence and between groups to establish whether treatment effects exist. Models that include the 30-day values also will be fit. Time period will be considered both as a continuous covariate (in days), as well as a categorical variable. Inferential interest will focus on treatment by time interaction. These models will also be used to explore the relationship between the level of P2Y12 inhibition and the reduction in inflammatory monocytes between treatments. This relationship could be different given that Ticagrelor is not only a more potent P2Y12 antagonist as compared with clopidogrel but may also have a unique dual mode of action; P2Y12 antagonism complemented with adenosine uptake inhibition.

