5.4 Time point/frame of measurement for primary variable(s)

The primary endpoints will be assessed 1 day after study drug initiation and TAVR. Measurements taken at 7 and 30 days after TAVR will be considered secondary/exploratory.

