5.6 Power Calculation and Sample Size Estimate

Our power calculation is based upon the inflammatory co-primary endpoint, using our preliminary data. In preliminary studies of 25 patients undergoing TAVR, the mean proportion of inflammatory monocytes 1 days after TAVR was 20.0% with a standard deviation of 5.0 %. Thus, a total of 60 patients, randomized 30:30 would be expected to have 80% power to detect an absolute effect of 4% (i.e. ticagrelor treated patients having 16 % percent inflammatory monocytes), using a two sided t-test with Type I error of 0.025. Note that we are using Bonferroni correction, to account for two primary outcomes. We expect dropout of randomized patients to be less than 10% prior to the 1 day blood draw. All randomized patients will be analyzed using an intention to treat analysis. We will assess the missing completely at random assumption by comparing results with analyses derived by assuming that the data is missing at random (MAR), and use of multiple imputation approaches.

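### The primary day-1 t-test has no rule for a missing value and ignores the baseline draw; a baseline-adjusted primary comparison would come closer to the all-randomised promise at almost no cost

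*Combined protocol and SAP*

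**What the plan says.** Two statements set the analysis population. Section 5.3 opens with "All endpoints will be determined according to an intention to treat analysis", and Section 5.6 adds "All randomized patients will be analyzed using an intention to treat analysis".

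For both co-primary endpoints (PRU and the percentage of inflammatory monocytes), Section 5.3 specifies an "independent samples t-test (or non-parametric test as appropriate), with significance declared for p-values <0.025". It names no covariate and no rule for a patient without a value. Section 5.4 fixes the time point: "The primary endpoints will be assessed 1 day after study drug initiation and TAVR".

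Section 5.6 anticipates some loss: "We expect dropout of randomized patients to be less than 10% prior to the 1 day blood draw". Its response is "We will assess the missing completely at random assumption by comparing results with analyses derived by assuming that the data is missing at random", together with multiple imputation. It gives no imputation model, no list of variables, and no statement of which result stands if the analyses differ.

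Two other features matter here. Section 5.2 schedules a baseline draw before TAVR and draws at 24 hours, 7 days and 30 days. Section 5.3 already plans longitudinal mixed models of the monocyte percentage, labelled exploratory, within and between groups.

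**The concern.** A two-sample test on day-1 values needs a day-1 value from each patient it counts. By naming MCAR as the assumption to be assessed, Section 5.6 implies that the primary result is a complete-case analysis, with the missing-at-random and imputation results serving only as comparators. On that reading, the promise to analyse everyone randomised is not met by the analysis that decides the trial.

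Section 5.8 has envelopes opened on or before the start of TAVR, so a randomised patient could lose the day-1 value through a cancelled or complicated procedure. Such loss could plausibly relate to inflammatory state, although the documents report no data on it. If it also differed between arms, the unadjusted difference would be shifted.

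Two further things are at stake. In an open-label trial, having no rule for conflicting results leaves that choice until the results are seen. And the baseline value, which could both protect against baseline-driven loss and sharpen the estimate, goes unused in the primary test.

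**Working it through.** **Inputs from the documents.** 30 patients per arm, control mean 20.0%, SD 5.0, difference 4 points, two-sided alpha 0.025 per endpoint, and dropout below 10% before day 1 (all Section 5.6). Below 10% of 60 means at most 5 patients.

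**Assumptions, not in the documents.** Correlation ρ between baseline and day-1 values of 0.3, 0.5 or 0.7; 3 of 30 lost per arm (6 in all, slightly more than the plan expects); ticagrelor losses drawn from the top third of baseline; clopidogrel losses random. Differences are ticagrelor minus clopidogrel, with a true value of −4. PRU is not worked, because the plan gives no effect size for it.

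**1. The plan's own figure.** Power = Φ(δ / (σ√(2/n)) − z), with z = 2.241.
- n = 30: 4 / (5√(2/30)) = 3.098, and Φ(3.098 − 2.241) = 0.804. The stated 80% reproduces (0.785 by the noncentral t).
- n = 27: 4 / 1.361 = 2.939, and Φ(0.698) = 0.757 (0.735 by the noncentral t).

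The 80% therefore takes all 60 patients as observed.

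**2. Loss that depends on baseline, in one arm only.** The top third of a normal distribution averages 1.09 SD above the mean. Removing 3 such patients lowers the mean baseline of the remaining 27 by 3 × 1.09 / 27 = 0.121 SD. The day-1 mean then falls by 0.121 × ρ × 5.

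| ρ | Shift | t-test estimate | Relative excess |
|---|---|---|---|
| 0.3 | 0.18 | −4.18 | 4.5% |
| 0.5 | 0.30 | −4.30 | 7.6% |
| 0.7 | 0.42 | −4.42 | 10.6% |

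Simulation of 4,000 trials per setting gave −4.18, −4.29 and −4.41. Baseline-adjusted analysis returned −4.0 throughout.

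With 5 lost (2 ticagrelor, 3 clopidogrel) and ρ = 0.5, the shift is 2 × 1.09 / 28 × 0.5 × 5 = 0.19, giving −4.19.

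**3. The same top-third loss in both arms.** The shifts cancel. The simulated t-test estimate was −3.99 to −4.02, whether loss depended on baseline or on the day-1 value.

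**4. Loss that depends on the unseen day-1 value, in the ticagrelor arm only.** Simulated results for ρ = 0.3, 0.5 and 0.7:
- Complete case: −4.56, −4.58, −4.56.
- Missing-at-random imputation: −4.50, −4.43, −4.28.
- Bias remaining after imputation: 0.50/0.56 = 89%, 0.43/0.58 = 74%, 0.28/0.56 = 50%.
- Gap between the two estimates: 0.06, 0.15, 0.28.

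Under true MCAR, that gap varies from trial to trial with an SD of 0.15, 0.23 and 0.31. The average gap under harmful loss is thus no larger than chance variation, and one trial of 60 could not tell the two apart.

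**5. Precision gained by adjustment.** With 27 per arm, the SE of the t-test difference is 5√(2/27) = 1.36. Adjustment multiplies it by about √(1 − ρ²), giving 1.30, 1.18 and 0.97. The formula in step 1 then gives power of about 0.80, 0.88 and 0.97, against 0.757 unadjusted.

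**The case against.** **The bias rests on different loss mechanisms by arm.** Nothing in the documents supports such a difference, and cancelled or complicated procedures would affect both arms. This stands. A reader might infer that the t-test is unbiased only under MCAR; step 3 shows that this is not so for the treatment difference.

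**Even then, the bias is small.** Against an SE of 1.36, a shift of 0.18 to 0.42 is 0.13 to 0.31 SE, and the expected loss is slightly below the case worked. This also stands, and it keeps the point minor.

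**The plan says assess, not validate.** A reader might infer that the plan claims to prove MCAR and that the comparison should be deleted. The text makes no such claim. Disagreement between the analyses would be evidence against MCAR, so the comparison is worth keeping.

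**Multiple imputation need not be primary.** A reader might infer that promoting it is required. With under 10% loss that is largely a preference, and on the figures in step 4 it leaves half to nearly 90% of the bias when loss depends on the unseen value.

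**No section says that patients are dropped.** This is correct: a t-test can be run on imputed data, and the complete-case reading is inferred from the MCAR wording and the absence of a rule. The exploratory mixed models would also retain patients with a baseline but no day-1 value. What survives is that the primary handling is unstated and that the model which would retain these patients is not the primary one.

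**Conclusion.** The point holds in limited form and is minor. The plan promises an analysis of everyone randomised, while its primary test, as implied, uses only patients with a day-1 value and makes no use of baseline. If loss depends on baseline and differs by arm, the estimate is about 4% to 11% too large at 3 of 30 lost per arm and correlations of 0.3 to 0.7. With like loss in both arms there is no bias. The stronger case for change is that adjustment removes the baseline-driven bias and also lowers the SE, from 1.36 to between 1.30 and 0.97 at the assumed correlations, whether or not loss is informative.

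The documents do not show that the primary result will be biased. Nor does adjustment cure loss driven by the unseen day-1 value; that needs its own sensitivity analysis.

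**What to change.** - Make the primary comparison of each co-primary endpoint baseline-adjusted, by assigned arm, at two-sided 0.025. Use ANCOVA, or the equivalent day-1 contrast from a longitudinal model of the kind Section 5.3 already plans. The longitudinal form is closer to the promise in Section 5.6, because it keeps randomised patients who have a baseline but no day-1 value; ANCOVA alone does not.
- Define baseline as a sample drawn before the first study dose. Section 5.2 says only that it precedes TAVR, and the Synopsis starts study drug that same morning.
- Keep the unadjusted t-test and the planned multiple imputation as sensitivity analyses, and specify the imputation model and its variables. State in advance that the adjusted result stands if they differ.
- Add a delta-adjusted (missing not at random) sensitivity analysis.
- Keep the MCAR versus missing-at-random comparison, but say that agreement does not confirm MCAR.

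The cost is plan wording and a little programming; no additional draw is needed. The downside is that the primary result then depends on a simple stated model rather than a bare two-sample test.

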5.7 Interruption or Discontinuation of treatment

Neither erroneous randomization of subject in the presence of exclusion criteria or non-fulfilment of inclusion criteria nor a post-randomization change in health status that results in the subject meeting one or more of the exclusion criteria should automatically lead to the interruption or permanent discontinuation of the assigned therapies, unless continuing the medications places the subject at undue risk as determined by the investigator. Such situations though very rare, may occur and should be handled on a case-by-case basis. Compliance with study drug medication will be assessed at day 1, 7, and 30. Drug supplies for each subject will be inventoried and reconciled throughout the study. Any discrepancies between actual and expected amount of study medication will be discussed with the subject at the time of the visit, and any explanation will be documented in the source records and captured in the eCRF. Subjects will return empty study drug containers and unused study drug visits. Study assigned therapies may be temporarily discontinued at the discretion of the treating physician. Subjects can resume the assigned therapy as soon as the treating physician considers it safe to do so. The reason for discontinuation of the assigned therapy will be recorded in the eCRF and in the subject's medical records. The decision to restart or permanently withdraw study medication is at the discretion of the investigator.

5.8 Treatment assignment

Randomization will be performed via seal envelop system. Opaque envelopes (60) will be filled with a sheet of paper in which Ticagrelor (30) or Clopidogrel (30) is written and envelopes are to be opened after informed consent is received and on or before the start of the TAVR such that study drug initiation occurs prior to TAVR. Randomization envelops are stored securely at the Clinical trials office at University Hospitals (UH).

5.9 Blinding

This trial is an open label trial and patients are not blinded. The laboratory staff will receive study samples containing patient study identification numbers but without any identifiers with regard to treatment assignment. Similarly, the analysis of flow cytometric data will be done by laboratory staff blinded to treatment assignment.

5.10. Drug logistics and accountability

Ticagrelor and Clopidogrel will be stored at the investigational pharmacy at University Hospitals Cleveland Medical Center in accordance with GCP and GMP requirements and according to the

product label. Receipt, distribution, return, and destruction (if any) of study medications will be properly documented.

5.11 Prior and concomitant therapy

All ongoing medications at screening and used during the study (prescription and over-the counter), including adjunct therapy or medical devices, will be recorded in the appropriate section of the eCRF throughout the study. Use of ASA and clopidogrel or any other P2Y12 inhibitor prior and during TAVR procedure should also be recorded. It is advised that the appropriate local and national guideline recommendations are followed for any concomitant medications. Concomitant medication will be evaluated when considering AE causal relationship.

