Inflammation and Thrombosis in Patients With Severe Aortic Stenosis After
Transcatheter Aortic Valve Replacement (TAVR)

NCT02486367

January 31, 2019

Supplementary Clinical Study Protocol

Title: Platelet and Monocyte Activation After Transcatheter Aortic Valve Replacement (POTENT-TAVR)

Subtitle: POTENT-TAVR: A Mechanistic Randomized Trial of Ticagrelor versus Clopidogrel

Table of Contents

1. Cover page	2
2. Synopsis.....	3
3. Introductory Background.....	4
4. Study objectives.....	6
5. Study design.....	7
6. References.....	12

1. Cover page

Title: Platelet and Monocyte Activation After Transcatheter Aortic Valve Replacement (POTENT-TAVR): POTENT-TAVR: A Mechanistic Randomized Trial of Ticagrelor versus Clopidogrel

Acronym: POTENT_TAVR

Test drug: Ticagrelor

Active Control: Clopidogrel

Clinical study phase: Phase 4

Sponsor: AstraZeneca

Principal Investigator:

[name]

Associate Professor of Medicine

Case Western Reserve School of Medicine

[name]

[contact]

Compliance Statement:

The study will be conducted in compliance with the protocol and any applicable regulatory requirements.

Confidentiality

The information provided in this document is strictly confidential and is intended solely for the guidance of clinical investigation. Reproduction or disclosure of this document - whether in part or in full - to parties not associated with the clinical investigation, or its use for any other purpose, without the prior written consent is not permitted.

2. Synopsis

Title: Platelet and Monocyte Activation After Transcatheter Aortic Valve Replacement (POTENT-TAVR)

Clinical study phase: Phase 4

Study objective(s): 1. To determine whether high-potency ADP receptor blockade reduces measures of platelet activation in patients after TAVR. 2. To determine whether high-potency ADP receptor blockade mitigates the pro-thrombotic inflammatory response observed after TAVR.

Test drug: Ticagrelor

Dose: 90mg twice daily

Route of administration: Oral

Duration of treatment: The first dose of Ticagrelor will be started (180mg load) the morning of planned TAVR. Treatment will continue for 30 days.

Active Comparator: Clopidogrel

Dose: 75 mg once daily

Route of administration: Oral

Duration of treatment: The first dose of Clopidogrel will be given (300 mg load if P2Y12 naïve or 75mg if P2Y12 non-naïve) the morning of planned TAVR. Treatment will continue for 30 days.

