The central hypothesis of our proposal is that TAVR-induced injury of the diseased native aortic valve leads to platelet deposition and inflammatory cell activation that can be attenuated by the potent anti-platelet and/or pleiotropic effects of ticagrelor. We propose a single center, prospective randomized trial to test the following specific aims:

1. **To determine whether high-potency ADP receptor blockade reduces measures of platelet activation in patients after TAVR.**
2. **To determine whether high-potency ADP receptor blockade mitigates the pro-thrombotic inflammatory response observed after TAVR.**

The co-primary study endpoints will be 1) platelet responsiveness as measured by the VerifyNow assay (platelet reactivity units, PRU) and 2) the proportion of inflammatory monocytes by polychromatic flow cytometry 1 day after TAVR. Secondary endpoints will include other measures of thrombotic and immunologic activation.

5. Study design

This is a single center, prospective, randomized, open label trial with blinded endpoint evaluation.

5.1 Screening, entry, and randomization:

Patients will be screened for inclusion/exclusion criteria as part of their pre-TAVR clinical evaluation (See Table 1). We plan to screen 150 patients per year, of whom 100 are expected to go on to TAVR. We will continue enrollment until 60 patients are randomized. All patients will be required to sign informed consent prior to planned TAVR. The scheme for a participant's movement through the trial is shown in figure 2.

Patients will be randomized in a 1:1 fashion (n=60) to either continue Clopidogrel (300mg load, 75mg daily) or begin Ticagrelor. Patients will receive a 180mg load followed by 90mg twice daily for one month. This will be an open label design given the different frequency of dosing. Decisions regarding the discontinuance of dual anti-platelet therapy after randomization will be at the discretion of the treating physician.

Patients will be seen at 30 days post TAVR per routine clinical practice. At this time, the final blood draw will be obtained. The occurrence of MACE and bleeding events will be determined by history and corroborated by examining relevant medical records. Patients will revert to clopidogrel therapy at this time and the duration of dual anti-platelet therapy will be left to the discretion of the treating physician.

5.2 Blood Biomarker Procurement:

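### Prior P2Y12 inhibitor use is recorded but used nowhere: no eligibility criterion, no stratification and no adjustment in the two day-1 primary comparisons

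*Combined protocol and SAP*

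**What the plan says.** Three places describe P2Y12 treatment before entry, each differently. The synopsis makes the first clopidogrel dose depend on prior exposure ("300 mg load if P2Y12 naïve or 75mg if P2Y12 non-naïve"), so both kinds of patient are expected, and it does not say which earlier agents count as exposure. Section 5.1 randomizes patients to "either continue Clopidogrel (300mg load, 75mg daily) or begin Ticagrelor", with no such split. Section 5.11 says "Use of ASA and clopidogrel or any other P2Y12 inhibitor prior and during TAVR procedure should also be recorded" and attaches no further use to that record.

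Table 1 and the matching synopsis list have 4 inclusion and 13 exclusion criteria. None concerns prior or current P2Y12 inhibitor use; exclusion 8 covers allergy only. Section 5.8 describes a single allocation set: "Opaque envelopes (60) will be filled with a sheet of paper in which Ticagrelor (30) or Clopidogrel (30) is written". Section 5.3 compares PRU and the percentage of inflammatory monocytes at day 1 by an independent-samples t-test, or a non-parametric test, each at 0.025. No stratum, covariate or subgroup for prior P2Y12 use appears in either document part.

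**The concern.** PRU measures P2Y12-dependent platelet reactivity, so P2Y12 treatment before entry is an obvious prognostic factor for that co-primary endpoint in a sample taken about 24 hours after study drug starts. For monocytes the link is indirect: it depends on the hypothesis in section 3 that monocyte activation is partly mediated by platelet-monocyte interaction.

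Two things are at stake. First, a mixture of naive and pretreated patients adds between-patient variance that the unadjusted tests leave in the error term. Second, with 60 patients and no stratification the arms can differ noticeably in pretreatment. The trial is mechanistic and open label, so a visible imbalance in prior P2Y12 exposure would invite argument about what the PRU result means. An adjustment added after the data are seen would carry less weight than one written down now.

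**Working it through.** **1. The plan's own power figure.** Section 5.6 gives a day-1 mean that "was 20.0% with a standard deviation of 5.0" (percent), and says that "a total of 60 patients, randomized 30:30 would be expected to have 80% power to detect an absolute effect of 4" percentage points, "using a two sided t-test with Type I error of 0.025". It explains the level: "Note that we are using Bonferroni correction, to account for two primary outcomes".
- Standard error of the difference = 5 × √(2/30) = 1.291.
- Standardized effect = 4 / 1.291 = 3.098.
- Normal approximation: Φ(3.098 − 2.241) = 80.4%.
- Exact noncentral t on 58 degrees of freedom: 78.5%.

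The stated 80% reproduces, with no slack.

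**2. Chance imbalance.** Under one 30:30 set, the number of pretreated patients in one arm is hypergeometric (60 patients, K pretreated, 30 drawn). The table gives the probability that the arms differ by at least 6 patients, which is 6/30 = 20 percentage points. K is an assumption.

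| Pretreated, of 60 | Probability of a difference of 6 or more |
|---|---|
| 12 | 10.4% |
| 18 | 15.8% |
| 20 | 17.0% |
| 30 | 19.6% |

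**3. What such an imbalance could do to PRU.** Section 3 gives an interquartile range of 164.8 to 290.3 in 28 clopidogrel-treated patients after TAVR. Assuming normality, SD ≈ (290.3 − 164.8)/1.349 = 93.0, and the standard error of the difference is 93.0 × √(2/30) = 24.0. Suppose pretreatment shifts day-1 PRU by δ units, equally in both arms (assumption). A 20-point imbalance then moves the contrast by 0.20δ. The share of variance due to pretreatment is p(1 − p)δ²/93.0², with p the pretreated share.

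| δ (assumed) | Shift in contrast | In standard errors | Variance share, p = 1/3 | Variance share, p = 1/2 |
|---|---|---|---|---|
| 25 | 5 | 0.2 | 1.6% | 1.8% |
| 50 | 10 | 0.4 | 6.4% | 7.2% |
| 100 | 20 | 0.8 | 25.7% | 28.9% |

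The effect runs from negligible to material, and the documents do not say where in that range it lies.

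**4. Dilution, if users of other agents enter.** If a fraction f of both arms shows no between-arm contrast at day 1 (assumption), the expected monocyte difference is 4(1 − f). Exact t power with SD 5 and 30 per arm:

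| f (assumed) | Expected difference | Power |
|---|---|---|
| 0 | 4.00 | 78.5% |
| 1% | 3.96 | 77.6% |
| 2% | 3.92 | 76.7% |
| 5% | 3.80 | 73.8% |
| 10% | 3.60 | 68.7% |

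This is an illustration only. The documents give neither f nor any time for an earlier agent's effect to wear off.

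**The case against.** The strongest reply is that randomization already deals with this. Prior use is equal in expectation, chance imbalance is part of the stated error rate, and leaving a 60-patient mechanistic trial unstratified is a common choice. That stands: type I error is preserved and an imbalance probability is not a bias. On the assumed shifts above, a 20-point imbalance moves the PRU contrast by less than one standard error, so it has not been shown that imbalance could by itself explain a positive result. What the reply leaves open is precision, and the value of settling the adjustment in advance.

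A reader might go further and infer that patients already on ticagrelor or prasugrel will be assigned to clopidogrel, with carry-over into both primary endpoints. The documents do not support that. Section 5.11 is a recording instruction covering use before and during the procedure; it does not describe who enters. Section 5.1, with patients continuing clopidogrel or beginning ticagrelor and all reverting to clopidogrel at 30 days, points to entrants who are naive or on clopidogrel. No offset times are given, and carry-over into monocytes would also need the trial's untested hypothesis to be true. What remains is that no written criterion rules such patients out.

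It can also be said that baseline blood and prior medication are collected, so a sensitivity analysis is possible later. It is possible, but section 5.3 does not plan one.

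**Conclusion.** The point holds as a gap in the use of prior P2Y12 status. The plan expects a naive and non-naive mix, records it, and then ignores it in eligibility, allocation and the primary analysis. The consequence is added variance and a chance of noticeable imbalance: 17% to 20% for a difference of 6 or more patients if 20 to 30 of the 60 are pretreated, a share the documents do not state. The link is direct for PRU and conditional on the trial's hypothesis for monocytes. The test's validity is not in question. Dilution by carry-over remains a possibility of unknown frequency and should not be reported as something the plan produces. Adjustment is worth making because it is cheap and uses data already collected, not because the present test is wrong.

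**What to change.** In section 5.3, prespecify each day-1 primary comparison as a linear model with treatment and prior P2Y12 status at entry (naive, clopidogrel, other agent), taken from the section 5.11 record, with the treatment effect still tested at 0.025. State in advance how a very small or empty third category will be merged. The cost is that a model with one categorical covariate, using at most two degrees of freedom, replaces the plain t-test, and the non-parametric alternative must be restated to match.

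Optionally, stratify the envelopes in section 5.8 by naive versus pretreated. Because the split is unknown, two fixed stacks cut from 60 envelopes could run out unevenly, so blocked sets with spare envelopes are needed. The costs are extra envelopes, arms that may not be exactly 30:30, and more predictable assignments in a single-center open-label trial if blocks are small.

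Reconcile the synopsis, section 5.1 and section 5.11 on which prior P2Y12 agents are eligible, and carry the answer into Table 1. That decision belongs to the sponsor and the investigator; no washout window or dosing rule is proposed here.
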